6.5.2.1 Dose adjustments for QTcF prolongation

If QTcF >500 msec or QTcF prolongation >60 msec from baseline is observed at any point during study treatment, and confirmed, the below guidance must be followed:

1. Assess the quality of the ECG recording and the QT value and repeat if needed
2. Interrupt study treatment until confirmed resolution of QTcF and as per dose reduction guidelines for non-hematological AEs.
3. Determine the serum electrolyte levels (in particular hypokalemia and hypomagnesemia). If abnormal, correct abnormalities before resuming study treatment.
4. Review concomitant medication associated with QT prolongation, including drugs with a “Known”, “Possible”, or “Conditional risk of Torsades de Pointes” (refer to www.crediblemeds.org/), and drugs with the potential to increase the risk of study drug exposure related QT prolongation.
5. Check the dosing schedule and treatment compliance

After confirming ECG reading at site, if QTcF > 500 msec

- Interrupt study treatment
- Repeat ECG and confirm ECG diagnosis by a cardiologist or central ECG lab
- If QTcF confirmed > 500 msec:
 - Correct electrolytes, eliminate culprit concomitant treatments, and identify clinical conditions that could potentially prolong the QT as per the ECG and QTc Clinical Safety Standards Guidelines
 - Consult with a cardiologist (or qualified specialist)
 - Increase cardiac monitoring as indicated, until the QTcF returns to ≤ 480 msec
- After resolution to ≤ 480 msec, consider re-introducing treatment at reduced dose, and increase ECG monitoring (e.g., pre dose and 2 hours post dose after one week and two weeks of treatment re-introduction)
- If QTcF remains ≤ 500 msec after dose reduction, continue planned ECG monitoring during subsequent treatment
- If QTcF recurs > 500 msec after dose reduction, discontinue subject from trial

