5.2 Exclusion criteria

Patients eligible for this study must not meet any of the following criteria:

1. Known second chronic phase of CML after previous progression to AP/BC
2. Previous treatment with a hematopoietic stem-cell transplantation
3. Cardiac or cardiac repolarization abnormality, including any of the following:
 - History within 6 months prior to starting study treatment of myocardial infarction (MI), angina pectoris, coronary artery bypass graft (CABG)
 - Clinically significant cardiac arrhythmias (e.g., ventricular tachycardia), complete left bundle branch block, high-grade AV block (e.g., bifascicular block, Mobitz type II and third degree AV block)
 - QTcF at screening ≥ 450 msec (male patients), ≥ 460 msec (female patients)

- Long QT syndrome, family history of idiopathic sudden death or congenital long QT syndrome, or any of the following:
 - Risk factors for Torsades de Pointes (TdP) including uncorrected hypokalemia or hypomagnesemia, history of cardiac failure, or history of clinically significant/symptomatic bradycardia
 - Concomitant medication(s) with a “Known risk of Torsades de Pointes” per www.crediblemeds.org/ that cannot be discontinued or replaced 7 days prior to starting study drug by safe alternative medication.
 - Inability to determine the QTcF interval
- 4. Severe and/or uncontrolled concurrent medical disease that in the opinion of the investigator could cause unacceptable safety risks or compromise compliance with the protocol (e.g. uncontrolled diabetes, active or uncontrolled infection, pulmonary hypertension)
- 5. History of acute pancreatitis within 1 year of study entry or past medical history of chronic pancreatitis
- 6. Known presence of significant congenital or acquired bleeding disorder unrelated to cancer
- 7. History of other active malignancy within 3 years prior to study entry with the exception of previous or concomitant basal cell skin cancer and previous carcinoma in situ treated curatively
- 8. Impairment of gastrointestinal (GI) function or GI disease that may significantly alter the absorption of study drug (e.g. ulcerative disease, uncontrolled nausea, vomiting, diarrhea, malabsorption syndrome, small bowel resection, or gastric bypass surgery)
- 9. Previous treatment with or known/ suspected hypersensitivity to asciminib or any of its excipients.

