| Grade 2 (ANC < 1.5 – | Recommendation: Maintain dose level |

| Dose modifications for asciminib | |
|---|--|
| Please note that if a patient requires a dose interruption of > 28 days for each toxicity, then the patient must be discontinued from the study treatment | |
| Worst toxicity CTCAE Grade 5 | Asciminib |
| 1.0 x 10 ⁹ /L) | |
| Grade 3 (ANC < 1.0 – 0.5 x 10 ⁹ /L) | Mandatory: Hold dose until resolved to ≤ Grade 2 (recheck CBC 2x/week), then: if resolved in ≤ 14 days, then maintain dose level If resolved in > 14 days, then reduce dose ↓ 1 dose level |
| Grade 4 (ANC < 0.5 x 10 ⁹ /L) | Mandatory: Hold dose until resolved to ≤ Grade 2, (recheck CBC 2x/week), then: if resolved in ≤ 14 days, then maintain dose level if resolved in > 14 days, then reduce dose ↓ 1 dose level |
| Febrile neutropenia (ANC < 1.0 x 10 ⁹ /L, fever ≥ 38.5°C) | Mandatory: Hold dose until resolved, then reduce dose ↓ 1 dose level |
| Thrombocytopenia | |
| Grade 1 (PLT < LLN – 75 X 10 ⁹ /L) | Recommendation: Maintain dose level |
| Grade 2 (PLT < 75 - 50 x 10 ⁹ /L) | Recommendation: Maintain dose level |

| Dose modifications for asciminib | |
|---|---|
| Please note that if a patient requires a dose interruption of > 28 days for each toxicity, then the patient must be discontinued from the study treatment | |
| Worst toxicity CTCAE Grade 5 | Asciminib |
| Grade 3 (PLT < 50 - 25 x 10 ⁹ /L) | Mandatory: Hold dose until resolved to ≤ Grade 2 (recheck CBC 2x/week), then: if resolved in ≤ 14 days, then maintain dose level if resolved in > 14 days, then reduce dose ↓ 1 dose level |
| Grade 4 (PLT < 25 x 10 ⁹ /L) | Mandatory: Hold dose until resolved to ≤ Grade 2 (recheck CBC 2x/week), then: if resolved in ≤ 14 days, then maintain dose level if resolved in > 14 days, then reduce dose ↓ 1 dose level |
| Recurrence of all cytopenias | Recommendation: For recurrent Grade 3-4 cytopenias: If resolved to ≤ Grade 2 in ≤ 14 days, then maintain dose level If resolved in > 14 days, then reduce asciminib and imatinib dose ↓ 1 dose level |
| Non-hematologic adverse reactions except where further specified in individual sections | |
| Grade 1 | Recommendation: Maintain dose level |
| Grade 2 | Recommendation: Hold dose until resolved to ≤ Grade 1, then maintain dose level |
| Grade 3 | Mandatory: Hold dose until resolved to ≤ Grade 1, then reduce dose ↓ 1 dose level |
| Grade 4 | Mandatory: Permanently discontinue patient from study drug treatment. |
| Investigations (Renal) | |

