| Grade 3 | Recommendation: Hold dose until resolved to ≤ grade 1, then : If resolved in ≤ 7 days, then maintain dose level If resolved in > 7 days, then reduce dose ↓ 1 dose level |
| 
All dose modifications should be based on the worst preceding toxicity.
 
^a Common Toxicity Criteria for Adverse Events (CTCAE Version 5)
 
^b Core LFTs consist of ALT, AST, total bilirubin (fractionated [direct and indirect], if total bilirubin > 2.0 x ULN), and alkaline phosphatase (fractionated [quantification of isoforms], if alkaline phosphatase > 2.0 x ULN).
 
^c “Combined” defined as total bilirubin increase to the defined threshold concurrently with ALT/AST increase to the defined threshold
 
If combined elevations of AST or ALT and total bilirubin do not meet the defined thresholds, please follow the instructions for isolated elevation of total bilirubin and isolated elevation of AST/ALT, and take a conservative action based on the degree of the elevations (e.g. discontinue treatment at the situation when hold dose is needed for one parameter and discontinue treatment is required for another parameter). After all elevations resolve to the defined thresholds that allow treatment re-initiation, re-start the treatment either at the same dose or at one dose lower if meeting a criterion for dose reduction
 
^d “Cholestasis” defined as ALP elevation (>2.0 x ULN and R value <2) in patients without bone metastasis, or elevation of ALP liver fraction in patients with bone metastasis
 
Note: The R value is calculated by dividing the ALT by the ALP, using multiples of the ULN for both values. It denotes whether the relative pattern of ALT and/or ALP elevation is due to cholestatic (R ≤ 2), hepatocellular (R ≥ 5), or mixed (R >2 and < 5) liver injury
 
* Note: If total bilirubin > 3.0 x ULN is due to the indirect (non-conjugated) component only, and hemolysis as the etiology has been ruled out as per institutional guidelines (e.g., review of peripheral blood smear and haptoglobin determination), then ↓ 1 dose level and continue treatment at the discretion of the investigator.
 
** Note: A CT scan or other imaging study to assess the pancreas, liver, and gallbladder must be performed within 1 week of the first occurrence of any ≥ Grade 3 of amylase and/or lipase. If asymptomatic Grade 2 elevations of lipase and/or amylase occur again at the reduced dose, patients will be discontinued permanently from study treatment.
 
*** Note: antidiarrheal medication is recommended at the first sign of abdominal cramping, loose stools or overt diarrhea
 | |

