Three serial ECGs (triplicate) should be performed ½ hour prior to dosing for pre-dose assessment. The serial ECGs should be taken approximately 5 minutes apart. All 3 ECGs for each time point should be sent to central ECG reader. Readings for QTc prolongation will be based on the average seen in the scans for each time point. The enrollment of patients has to be based on centrally assessed QTcF time. If one of the 3 serial ECGs prior to dosing on day 1 shows a QTcF \geq 450 msec (male) or \geq 460 msec (female) by automated reading, an immediate manual central reading must be requested by either contacting the medical monitor or by calling central ECG reader. The patient may not be dosed if the average of the manually read ECGs confirms a QTcF \geq 450 msec (male) or \geq 460 msec (female).

Dose adjustments in case of QT prolongation should be performed per [Section 6.5.2.1](#)

Additional unscheduled ECGs may be repeated at the discretion of the investigator at any time during the study as clinically indicated. Unscheduled ECGs with clinically significant findings should be collected in triplicate. Local cardiologist ECG assessment may also be performed at any time during the study at the discretion of the investigator.

All ECGs, including unscheduled triplicate safety ECGs with clinically relevant findings, collected during the study should be transmitted to the central core ECG laboratory for review.

The results of the centrally assessed ECGs are automatically transferred into the clinical database.

Clinically significant ECG abnormalities present at screening should be reported on the Medical History eCRF page. New or worsened clinically significant findings occurring after informed consent must be recorded on the Adverse Events eCRF page.

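### The 480 msec restart threshold after a QTcF above 500 msec is not reconciled with the protocol's own trigger of a rise above 60 msec from baseline

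*Protocol*

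**What the plan says.** Protocol section 6.5.2.1 opens with two triggers, either of which is enough. One is a confirmed QTcF above 500 msec. The other is relative: "QTcF prolongation >60 msec from baseline is observed at any point during study treatment, and confirmed, the below guidance must be followed".

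Five numbered steps follow for both triggers. Step 2 is the hold rule: "Interrupt study treatment until confirmed resolution of QTcF and as per dose reduction guidelines for non-hematological AEs". It gives no QTcF value. Step 3 requires abnormal electrolytes to be corrected before dosing resumes.

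A separate block then covers a QTcF above 500 msec. It asks for a repeat ECG, specialist consultation, removal of contributing drugs and closer monitoring. Its restart bullet reads: "After resolution to ≤ 480 msec, consider re-introducing treatment at reduced dose". This is the section's only numeric restart value, and it has no change-from-baseline condition.

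Table 6-2, to which step 2 leads, has no QTc row. Its general non-hematologic row for Grade 3 says "Hold dose until resolved to ≤ Grade 1, then reduce dose ↓ 1 dose level". Neither document prints the QTcF limits of that grade.

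Eligibility sets only an upper limit on QTcF: below 450 msec for men and 460 msec for women at screening (section 5.2). Section 8.3.2.1 repeats it on day 1: "The patient may not be dosed if the average of the manually read ECGs confirms a QTcF" at or above those values. There is no lower limit.

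**The concern.** A stop rule and its restart rule should be stated on the same scale, or one should say which prevails. Here the stop rule has an absolute and a relative arm, while the printed restart value is absolute only. A patient with a low baseline who passes 500 msec meets both arms at once, yet only the absolute arm has a number for recovery.

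Taken bullet by bullet, the section can treat the worse event more leniently. With a baseline of 400 msec, a patient who peaks at 465 msec (rise 65) must be interrupted. A patient who peaked at 510 msec may be considered for restart at 480 msec (rise 80). If QTcF then stayed at 480 msec on treatment, the opening rule would call for interruption again.

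What is at stake is consistent handling of patients who have already exceeded 500 msec: one site may restart where another holds. The liver rules in Table 6-2 anticipate a similar overlap. When combined elevations fall short of their joint threshold, sites are told to "take a conservative action based on the degree of the elevations". Section 6.5.2.1 has no such sentence.

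**Working it through.** The plan states no calculated figure on this point, so there is none to reproduce.

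**Inputs**
- Relative trigger: rise above 60 msec from baseline (Protocol 6.5.2.1, opening rule).
- Restart value: 480 msec or less (Protocol 6.5.2.1, block for QTcF above 500 msec).
- Permitted baseline: below 450 msec (men) or 460 msec (women) (Protocol 5.2 and 8.3.2.1).

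**Where the rules overlap.** A restart value r still meets the relative trigger when r − baseline > 60 and r ≤ 480. That is possible only if baseline + 60 < 480, so baseline < 420 msec. In whole msec:

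| Baseline | Trigger met above | Restart values in the overlap | Rise at 480 | Threshold min(480, baseline + 60) |
|---|---|---|---|---|
| 380 | 440 | 441–480 | 100 | 440 |
| 400 | 460 | 461–480 | 80 | 460 |
| 410 | 470 | 471–480 | 70 | 470 |
| 419 | 479 | 480 | 61 | 479 |
| 420 | 480 | none | 60 | 480 |
| 430 | 490 | none | 50 | 480 |

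All baselines below 420 msec are eligible, so the overlap can occur.

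**How often.** The patient must have a baseline below 420 msec and an event above 500 msec, so a rise of more than 500 − 420 = 80 msec. Such patients are a subset of those with any rise above 60 msec. Protocol section 1.1.2.2 reports no rise above 60 msec on asciminib monotherapy, and two new values above 500 msec. If both counts use the same baseline and QT measure, those two patients had baselines above 500 − 60 = 440 msec, outside the overlap.

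The number with ECG data behind the zero count is not given. The section mentions 150 patients on monotherapy, so I assume 150 and vary it downward. With zero events the two-sided 95% upper limit is 1 − 0.025^(1/n):
- n = 150: 2.4%, or 0.0243 × 115 = 2.8 of the planned 115 patients
- n = 120: 3.0%, or 0.0303 × 115 = 3.5
- n = 100: 3.6%, or 0.0362 × 115 = 4.2

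These limits are for any rise above 60 msec. The affected subset is smaller.

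**Analysis.** SAP section 2.6.5.1 classes notable QTcF values by absolute cut-offs (above 480 to 500 msec, and above 500 msec) and also summarizes change from baseline. The restart rule enters neither definition, and it plays no part in the sample size.

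**The case against.** The strongest reply is that the bullet does not stand alone. Steps 2 and 3 bind every patient who meets either trigger, and nothing says that the block for values above 500 msec replaces them. A patient still 80 msec above baseline has one of the two named events continuing, so a careful site could say that QTcF has not resolved. Step 2 also brings in the rule to hold until Grade 1 or lower, and a standard adopted by reference binds sites even if its limits are not printed. Finally, restart is only to be considered, at a reduced dose, with specialist input and added ECGs. A site that holds at 480 msec breaches nothing.

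Most of this stands, and it rules out two stronger readings. A reader might infer that restart rests on 480 msec alone. The documents do not support that, because steps 2 and 3 also apply. A reader might also infer that the later bullet, "If QTcF remains ≤ 500 msec after dose reduction, continue planned ECG monitoring during subsequent treatment", lets dosing go on at the reduced dose despite a rise above 60 msec. That fails too: the relative trigger applies at any point during treatment, and the bullet speaks only of ECG monitoring.

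What the reply does not remove is the ambiguity. Step 2 gives resolution no number, and the later block uses the same idea with 480 msec attached, so a site can reasonably take 480 msec as its meaning. Whether Grade 1 or lower excludes a rise above 60 msec cannot be settled from the protocol or SAP.

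**Conclusion.** The point holds as an ambiguity between two rules in one section. For baselines below 420 msec, the restart bullet can be read as allowing restart to be considered while the relative interruption trigger is still met, and step 2 can be read as forbidding it. The arithmetic is certain. How sites would read the section is not, and the ungiven grade limits could close the gap, so confidence is moderate.

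The point is minor. It concerns only patients with a low baseline and an event above 500 msec, and the earlier monotherapy data, as reported, show no patient with a rise above 60 msec. The upper limit of about 3 to 4 patients in 115 covers that wider group. It rests on an assumed 100 to 150 patients with ECGs and on the earlier experience carrying over to this trial's doses. No analysis or sample size figure is affected.

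**What to change.** In the restart bullet of Protocol section 6.5.2.1, insert *and ≤ 60 msec above baseline* directly after the 480 msec value. The threshold then becomes min(480, baseline + 60), as in the last column of the table above, and does not change for baselines of 420 msec or more. The bullet on values of 500 msec or less needs no edit.

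The cost is one phrase at the next amendment. No new ECGs are needed: triplicate, centrally read recordings are already collected and change from baseline is already summarized. The downside is that a very few patients may be held slightly longer before restart.

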| Start of the clinical trial | The start of the clinical trial is defined as the signature of the informed consent by the first participant |
| Study treatment | Any drug or combination of drugs or intervention administered to the study participants as part of the required study procedures; includes investigational drug(s), control(s) or background therapy |
| Study treatment discontinuation | When the participant permanently stops taking any of the study drug(s) prior to the defined study treatment completion date (if any) for any reason; may or may not also be the point/time of study discontinuation |
| Treatment arm/group | A treatment arm/group defines the dose and regimen or the combination, and may consist of 1 or more cohorts. |
| Treatment of interest | The treatment of interest and, as appropriate, the alternative treatment to which comparison will be made. These might be individual interventions, combinations of interventions administered concurrently, e.g. as add-on to standard of care, or might consist of an overall regimen involving a complex |

| | |
|-----------------------------------|--|
| | sequence of interventions. This is the treatment of interest used in describing the related clinical question of interest, which might or might not be the same as the study treatment. |
| Variable (or endpoint) | The variable (or endpoint) to be obtained for each participant that is required to address the clinical question. The specification of the variable might include whether the participant experiences an intercurrent event. |
| Victim drug | The drug that is affected by the drug-drug interaction |
| Withdrawal of study consent (WoC) | Withdrawal of consent from the study occurs only when a participant does not want to participate in the study any longer and does not allow any further collection of personal data |

Amendment 3 (22-Mar-2022)

At the time of this amendment 25 patient have been enrolled for the study

The primary purpose of this amendment is:

Per FDA guidance, the cohort allocation and asciminib dosage depends on T315I mutational status, and to ensure that patients with T315I negative status did not develop a detectable T315I mutation post mutation analysis and prior to receiving asciminib. Novartis recognizes that, in order to ensure patients have not acquired a new kinase domain mutation, such as T315I, before study drug treatment, eligible patients will now require having kinase domain mutation testing at Baseline.

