6.5.2 Dose modifications

For patients who do not tolerate the protocol-specified dosing schedule, dose interruptions and/or reductions are either recommended or mandated in order to allow the patient to continue the study treatment.

These dose modifications are summarized in [Table 6-2](#). The dose reduction indicated as “recommendations” is provided to assist investigators in the event the patient experiences toxicity. However, deviations from “mandatory” dose interruptions and/or reductions are not allowed and mandatory interruptions or reductions must be strictly followed. Re-escalation to asciminib 40 mg BID is permitted if a change in the patient’s individual benefit/risk assessment at the lower dose level is seen. Re-escalation will be allowed only once for any given patient. Permanent treatment discontinuation is mandatory for specific events indicated as such in [Table 6-2](#). Any dose changes must be recorded on the Dosage Administration Record eCRF.

A patient must discontinue treatment with Asciminib if, after treatment is resumed at a lower dose level, the toxicity recurs with the same or worse severity, except for recurrence of cytopenias ([Table 6-2](#)). If a patient requires a dose interruption of > 28 days for each non-hematologic toxicity, then the patient must be discontinued from the study treatment. If a hematologic toxicity (cytopenia Grade 3 or 4) lasts for more than 42 days without recovery to at least a Grade 2, despite TKI interruption and adequate management (including hematopoietic growth factors), then the patient must be discontinued from the study treatment.

These dose changes must be recorded on the appropriate case report form (CRF).

Table 6-2 Criteria for dose reduction / interruption and re-initiation of asciminib treatment for adverse drug reactions.

| Dose modifications for asciminib | |
|---|--|
| Please note that if a patient requires a dose interruption of > 28 days for each toxicity, then the patient must be discontinued from the study treatment | |
| Worst toxicity CTCAE Grade 5 | Asciminib |
| Investigations (Hematologic) If a hematologic toxicity (cytopenia Grade 3 or 4) lasts for more than 42 days without recovery to at least a Grade 2, despite TKI interruption and adequate management (including hematopoietic growth factors), then the patient must be discontinued from the study treatment. | |
| Neutropenia (ANC) | |
| Grade 1 (ANC < LLN – 1.5 x 10 ⁹ /L) | Recommendation: Maintain dose level |

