The Assessment Schedule ([Table 8-1](#)) lists all of the assessments when they are performed. All data obtained from these assessments must be supported in the participant's source documentation.

Participants should be seen for all visits/assessments as outlined in the assessment schedule ([Table 8-1](#)) or as close to the designated day/time as possible. Missed or rescheduled visits should not lead to automatic discontinuation. Participants who prematurely discontinue the study for any reason should be scheduled for a visit as soon as possible, at which time all of the assessments listed for the final visit will be performed. At this final visit, all dispensed investigational product should be reconciled, and the adverse event and concomitant medications recorded on the CRF.

[figure not shown]
No eCRF will be used as a source document.

(S) is defined as "Source"

[figure not shown]
(D) is defined as "Data Based"

Table 8-1 Assessment schedule

[figure not shown]
| Visit name | Category | Protocol Section 8 | Screening Phase | Treatment Phase | | | | | | | | | | | | | | | |
|------------------------------------|----------|--------------------|----------------------------------|-----------------|--------------|--------|--------|---------|---------|---------|---------|---------|---------|---------|---------|---------|---------|---------|--|
| | | | | Week 1 Day 1 | Week 2 Day 1 | Week 4 | Week 8 | Week 12 | Week 16 | Week 20 | Week 24 | Week 28 | Week 32 | Week 36 | Week 40 | Week 44 | Week 48 | Week 52 | |
| Obtain Informed Consent | D | | X (Screening window -56 days) | | | | | | | | | | | | | | | | |
| Eligibility checklist/registration | D | | X | | | | | | | | | | | | | | | | |
| Cohort Assignment | D | 6.3.2 | X | | | | | | | | | | | | | | | | |
| Demography | D | 8.2 | X | | | | | | | | | | | | | | | | |
| Inclusion/exclusion criteria | D | 5.1 | X | | | | | | | | | | | | | | | | |
| Medical History | D | 8.2 | X | | | | | | | | | | | | | | | | |
| Disease History | D | 8.2 | X | | | | | | | | | | | | | | | | |
| Mutation status | D | 8.2 | X | | | | | | | | | | | | | | | | |
| Prior antineoplastic therapy | D | 8.2 | X | | | | | | | | | | | | | | | | |
| Prior TKI therapy | D | 8.2 | X | | | | | | | | | | | | | | | | |

[figure not shown]
[figure not shown]
| Visit name | Category | Protocol Section 8 | Screening Phase Screening/ Baseline (Day -21 to -1) | Treatment Phase | | | | | | | | | | | | | | | |

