- Detection of new BCR-ABL1 mutations which potentially cause resistance to study treatment (asciminib) at any time after initiation of therapy
- Confirmed loss of MMR in 2 consecutive tests ([Section 8.5](#)) (BCR-ABL1 > 0.1%)
- In the event of disease progression the patient must be discontinued from the study treatment. The following events are considered disease progression.
 - CML-related death (any death during treatment or follow-up if the principal cause of death is marked as “study indication” in the eCRF by the investigator, or if the death occurred subsequent to documented progression to AP/BC and the cause of death is reported as “unknown” or not reported by the investigator).
 - Accelerated phase (AP) as defined by any of the following:
 - $\geq 15\%$ blasts in the peripheral blood or bone marrow aspirate, but $< 30\%$ blasts in the peripheral blood or bone marrow aspirate
 - $\geq 30\%$ blasts plus promyelocytes in peripheral blood or bone marrow aspirate
 - $\geq 20\%$ basophils in the peripheral blood
 - Thrombocytopenia ($< 100 \times 10^9/L$) that is unrelated to therapy
 - Blast crisis (BC) as defined by any of the following:
 - $\geq 30\%$ blasts in peripheral blood or bone marrow aspirate

If discontinuation of study treatment occurs, the investigator should make a reasonable effort to understand the primary reason for the subject’s premature discontinuation of study treatment and record this information.

Subjects who discontinue study treatment or who decide they do not wish to participate in the study further should NOT be considered withdrawn from the study UNLESS they withdraw their consent (see withdraw of informed consent section.). Where possible, they should return for the assessments indicated in the assessment schedule. If they fail to return for these assessments for unknown reasons, every effort (e.g. telephone, e-mail, letter) should be made to contact the subject/pre-designated contact as specified in the lost to follow-up section. This contact should preferably be done according to the study visit schedule.

If the subject cannot or is unwilling to attend any visit(s), the site staff should maintain regular telephone contact with the subject, or with a person pre-designated by the subject. This telephone contact should preferably be done according to the study visit schedule.

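### The QTcF recurrence rule removes the patient from the trial, while the protocol's other rules stop treatment only; this is a minor contradiction that could cost later progression and survival status in a very few patients

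*Protocol*

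**What the plan says.** Protocol Section 6.5.2.1 sets out guidance that it describes as compulsory when a confirmed QTcF exceeds 500 msec or has risen by more than 60 msec. For values above 500 msec, treatment is interrupted, the reading is confirmed, and re-introduction at a reduced dose may be considered once QTcF is 480 msec or less. The last bullet is "If QTcF recurs > 500 msec after dose reduction, discontinue subject from trial".

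The rules around it concern treatment:

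- Section 6.5.2, on any toxicity returning at the lower dose: the patient "must discontinue treatment with Asciminib if, after treatment is resumed at a lower dose level, the toxicity recurs with the same or worse severity" (cytopenias excepted).
- Table 6-2: its mandatory permanent stops end study drug only. It has no QTcF row, but step 2 of Section 6.5.2.1 sends QTcF handling to the dose guidelines for non-hematological events.
- Section 9.1.1: patients who stop treatment "should NOT be considered withdrawn from the study UNLESS they withdraw their consent". "Where possible, they should return for the assessments indicated in the assessment schedule"; if they cannot or will not attend, "the site staff should maintain regular telephone contact with the subject, or with a person pre-designated by the subject".
- Glossary: stopping treatment "may or may not also be the point/time of study discontinuation", so the two are separate events. Premature withdrawal is defined as the point after which no more assessments are planned.
- Section 8: "Participants who prematurely discontinue the study for any reason should be scheduled for a visit as soon as possible", with all final-visit assessments done then.

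**The concern.** Sites have two instructions for the same patient. The specific bullet says the patient leaves the trial. The general rule on study status says the patient stays and is still seen or telephoned. The protocol states no order of precedence.

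Later status is what could be lost. OS (Protocol Section 12.5.2.5) counts deaths after treatment has been discontinued, and PFS (12.5.2.4) counts progression to AP/BC or death from any cause. SAP Table 2-5 takes last-known-alive dates partly from a survival follow-up page. The visit columns of Table 8-1 end at the 30-day safety follow-up. For a patient who stops early, Section 9.1.1 is therefore the protocol text that keeps progression and survival status coming in after that point. A site that takes the bullet literally would not apply it.

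**Working it through.** The plan gives no figure for QTcF recurrence, so there is none to reproduce. The check has three parts.

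**1. Literal path against treatment-only path**

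| Step | Bullet read literally | Sections 6.5.2 and 9.1.1 |
|---|---|---|
| Asciminib | Stopped | Stopped |
| Visit on leaving | Final visit (Section 8) | End-of-treatment visit (Table 8-1) |
| AE/SAE follow-up for 30 days after last dose (6.5.3) | Yes | Yes |
| Follow-up of the QT event | Yes | Yes |
| Later scheduled assessments | None planned (glossary) | Where possible |
| Later telephone contact | None stated | Yes |

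The QT event is covered in both columns. Section 6.5.2.1 itself says "Increase cardiac monitoring as indicated, until the QTcF returns to ≤ 480 msec". Section 6.5.3 requires weekly follow-up for drug-related stops, for four weeks or until the event resolves or stabilises, whichever is first. Section 9.1.1 requires follow-up of related events, and Section 10.1.1 requires every adverse event to be followed until it resolves or is judged permanent. The columns differ only in the last two rows.

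**2. Progression records at risk per patient**

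Counting columns in the Progression Status row of Table 8-1, the first part of the table has marks at Weeks 12, 24 and 48. The second part has one more mark, which falls under Week 68 as the table was read. It may instead belong to the neighbouring end-of-treatment/early-discontinuation column: the amendment log describes progression status as captured there, and table columns can shift in PDF reading. A recurrence before Week 12 therefore puts three later marks at risk, or four if the last one is a Week 68 visit. If it is the end-of-treatment visit, it is completed on leaving under either reading, because Section 8 requires the final-visit assessments.

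**3. How many patients**

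Inputs: 2 new values above 500 msec, and 150 monotherapy patients (both Protocol Section 1.1.2.2, Safety); 115 planned patients (Section 12.9). One report per patient and the same incidence in this trial are assumed.

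- Incidence: 2/150 = 1.33%. Exact (Clopper-Pearson) 95% CI 0.162% to 4.733%.
- First events: 115 × 0.01333 = 1.53. Limits: 115 × 0.00162 = 0.19 and 115 × 0.04733 = 5.44.

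The documents give no share of first events that recur after dose reduction. Taking 10% to 50% purely as an assumption, expected patients = 115 × incidence × share:

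| Assumed share | At lower limit | At point estimate | At upper limit | P(0 or 1 patient), point estimate |
|---|---|---|---|---|
| 10% | 0.02 | 0.15 | 0.54 | 0.99 |
| 25% | 0.05 | 0.38 | 1.36 | 0.94 |
| 50% | 0.09 | 0.77 | 2.72 | 0.82 |

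The pooled incidence is rough. The two reports were at 80 mg QD and 120 mg QD. None occurred at 40 mg BID, where 0/35 has an exact upper limit of 1 − 0.025^(1/35) = 10.0%. The reports are not described as confirmed, whereas Section 6.5.2.1 requires confirmation and then only suggests considering re-introduction. Both steps would reduce the number who reach the bullet.

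**The case against.** The strongest reply is that Section 9.1.1 already settles the matter. It is the section on study status, and a patient stopped for recurrent QTcF has necessarily stopped treatment, so its rule applies. Context points the same way: the bullet sits under dose adjustments within dose modifications, and step 2 invokes treatment-only rules. The protocol also uses study discontinuation loosely elsewhere. Section 1.1.2.2 counts study discontinuations and then lists reasons leading to treatment discontinuation.

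Much of this stands. Many sites may well read the bullet as treatment only, which limits the loss. But that reading is an inference. No text says it, Section 9.1.1 does not address removal directed by another section, and the glossary keeps the two events apart.

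It is also fair that follow-up after treatment is thin for every early stopper, whatever the reason: Table 8-1 has no visit after the 30-day follow-up, and the Section 9.1.1 wording is soft. The bullet adds only a little to that. Where status is missing, SAP Section 2.8.3 censors PFS at the last study assessment and OS at the last contact.

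A reader might infer two stronger points that the documents do not support. One is that monitoring of the QT event would stop; the provisions compared above require it under either reading. The other is that PFS, OS or the primary safety summaries would be distorted; with fewer than one affected patient expected at the point estimate, that cannot be claimed.

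**Conclusion.** The rule is wrong as written: Section 6.5.2.1 contradicts Sections 6.5.2 and 9.1.1 and the treatment-only stops in Table 6-2. Severity is minor. The wording conflict is certain. The loss of data is only possible, and depends on a site taking the bullet literally.

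The size is about 1.5 first events in 115 patients (0.19 to 5.4 across the exact interval), with recurrences an unknown subset. Under the assumed 10% to 50% share, 0.15 to 0.77 patients are expected at the point estimate. This rests on the first-in-human incidence carrying over to these doses and on an unsourced recurrence share. For each affected patient with an early recurrence, the exposure is three or four scheduled progression records, depending on where the last mark in Table 8-1 belongs, plus survival status after the 30-day follow-up. Section 9.1.1 asks for return visits only where possible, so some of these might be missed in any case.

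**What to change.** In Section 6.5.2.1, keep the trigger in the last bullet and replace the action with: permanently discontinue study treatment; the patient remains in the study and is followed per Sections 6.5.3 and 9.1.1. The monitoring until QTcF is back to 480 msec or less stays as it is.

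The cost is one bullet in the next protocol amendment. It adds no visit or procedure, does not change when the drug stops, and leaves the sample size and the analyses as planned.
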